Appendix 10 Details of Futility Analysis

An unmasked interim analysis will be conducted for futility assessment by the DMC when approximately 50% of the total planned AC-determined NMO/NMOSD attacks occur in this study. This will be triggered when approximately 34 AC-determined NMO/NMOSD attacks occur in the ITT population. The assessment of futility will be based on predictive power, which is based on the average conditional power calculated at the observed treatment effect at the time of the interim analysis. The study will be considered futile if the predictive power is < 20% in both the ITT population and the AQP4-IgG seropositive cohort. Figure 12 provides estimated predictive power when observed treatment effect varies from 0 to 90% in relative reduction in risk of an AC-determined NMO/NMOSD attack in the ITT population. The 20% predictive power translates into a treatment effect of approximately 27%. A value of 50% and 90% predictive power will result in 43% and 60% treatment effects, respectively, which are minimally detectable treatment effect and target treatment effect for this study. The actual predictive power will be calculated based on observed data.

Figure 12 Estimated Predictive Power Against Observed Interim Treatment Effect When 50% of AC-determined NMO/NMOSD Attacks are Available

AC = Adjudication Committee; HR = hazard rate; NMO/NMOSD = neuromyelitis optica/neuromyelitis optica spectrum disorders

Appendix 11 Type I Error Control

To establish Type I error control, the primary endpoint, and the 4 secondary endpoints will be denoted by E1 through E5, respectively, as follows:

- E1: Time to AC-determined NMO/NMOSD attack
- E2: Worsening from baseline in EDSS at last visit during the RCP
- E3: Change from baseline in low-contrast visual acuity binocular score measured by low-contrast Landolt C Broken Rings Chart, at last visit during RCP
- E4: Cumulative total active MRI lesions (new Gd-enhancing or new/enlarging T2) during the RCP
- E5: Number of NMO/NMOSD-related in-patient hospitalizations

Based on 2 populations of interest (seropositive and ITT populations), this will result in testing 10 null hypotheses of no treatment effect labeled as follows (Table 21):

[figure not shown]
Table 21 List of Null Hypotheses Considered Under Multiplicity Adjustment Procedure

Hypothesis	Test
S1	Test E1 in seropositive subjects
S2	Test E2 in seropositive subjects
S3	Test E3 in seropositive subjects
S4	Test E4 in seropositive subjects
S5	Test E5 in seropositive subjects
O1	Test E1 in ITT population
O2	Test E2 in ITT population
O3	Test E3 in ITT population
O4	Test E4 in ITT population
O5	Test E5 in ITT population

The multiplicity adjustment strategy based on Bonferroni-based chain procedure (Bretz et al, 2009; Millen and Dmitrienko, 2011) for testing these 10 hypotheses is defined in Figure 13. Each hypothesis is represented by a rectangular box. The connections among the hypotheses are visualized using arrows. A solid arrow is used to define the decision path after a hypothesis is rejected, eg, the hypothesis O1 is tested if and only if the hypothesis S1 is rejected. The Bonferroni-based chain procedures are characterized by 2 rules:

- The alpha allocation rule specifies the initial distribution of the Type I error rate among the null hypotheses according to the relative importance of the null hypotheses
- The alpha propagation rule determines the process of re-distributing the available Type I error rate among the non-rejected null hypotheses after each rejection

Figure 13 **Multiplicity Adjustment Strategy**

The alpha allocation rule is specified in Table 22. Specifically, the null hypothesis S1 receives the initial weight of 1 (ie, it is tested at the full $\alpha = 0.05$) and the other null hypotheses receive zero weights. The alpha propagation rule is specified in Table 23. The alpha propagation rules are defined using transition parameters, eg, the first row in Table 23 shows that the fraction of the Type I error rate used in testing the null hypothesis S1 will be transferred to the null hypothesis O1 if the null hypothesis S1 is rejected. Similarly, if the null hypothesis O1 is rejected, the available Type I error rate will be split equally among the null hypotheses S2, S3, S4, and S5 (a quarter of the available Type I error rate will be allocated to each null hypothesis). The alpha allocation and alpha propagation rule uniquely define the Bonferroni-based chain procedure and the associated multiplicity-adjusted p-values can be computed using Algorithm 2 given in [Bretz et al \(2009\)](#).

Table 22 Alpha Allocation Rule

Hypothesis	Initial Alpha Allocation
S1	α
S2	0
S3	0
S4	0
S5	0
O1	0
O2	0
O3	0
O4	0
O5	0

Table 23 Alpha Propagation Rule

Hypothesis	S1	S2	S3	S4	S5	O1	O2	O3	O4	O5
S1	0	0	0	0	0	1	0	0	0	0
S2	0	0	0	0	0	0	1	0	0	0
S3	0	0	0	0	0	0	0	1	0	0
S4	0	0	0	0	0	0	0	0	1	0
S5	0	0	0	0	0	0	0	0	0	1
O1	0	1/4	1/4	1/4	1/4	0	0	0	0	0
O2	0	0	1/3	1/3	1/3	0	0	0	0	0
O3	0	1/3	0	1/3	1/3	0	0	0	0	0
O4	0	1/3	1/3	0	1/3	0	0	0	0	0
O5	0	1/3	1/3	1/3	0	0	0	0	0	0

Appendix 12 Assessment and Collection of Adverse Events

If an investigator learns of any SAEs, including death, at any time after a subject has completed the study and he/she considers there is a reasonable possibility that the event is related to MEDI-551, the investigator should notify the Sponsor.

Variables to be Collected for AEs and SAEs

AEs

The following variables will be collected for each AE:

- AE (verbatim)
- Date when the AE started and stopped
- Whether the AE is serious
- Investigator causality rating against the investigational product (yes or no)
- Action taken with regard to investigational product
- If AE caused the subject to be withdrawn from the study (yes or no)
- Outcome

SAEs

For SAEs, other variables will be collected, including treatment given for the event.

It is important to distinguish between serious and severe AEs. Severity is a measure of intensity, whereas, seriousness is defined by the criteria presented in Section 5.2. An AE of severe intensity need not necessarily be considered serious. For example, nausea that persists for several hours may be considered severe nausea, but not an SAE. On the other hand, a stroke that results in only a limited degree of disability may be considered a mild stroke, but it would become an SAE when it satisfies the criteria.

Causality

The investigator will assess the causal relationship between the investigational product and each AE, and answer 'yes' or 'no' to the question, 'Do you consider there is a reasonable possibility that the event may have been caused by the investigational product?'

For SAEs, the causal relationship will also be assessed for other medication and study procedures. For SAEs that could be associated with any study procedure, the causal relationship is implied as 'yes.'

AEs Based on Signs and Symptoms

All AEs spontaneously reported by the subject or care provider, or reported in response to the question, 'Have you had any health problems since the previous visit/you were last asked?', or

any AEs that were observed, will be collected and recorded in the eCRF. When collecting AEs, recording the diagnosis is preferred to a listing of signs and symptoms. However, if a diagnosis is known and there are other signs or symptoms that are not generally considered part of the diagnosis, the diagnosis and each sign or symptom should be recorded separately.

AEs Based on Examinations and Tests

The results of protocol-mandated laboratory tests and vital signs will be summarized in the clinical study report. Deterioration in protocol-mandated laboratory test values or vital signs compared to baseline should only be reported as AEs if they fulfill any of the SAE criteria, or are a reason for the discontinuation of treatment with the investigational product.

If deterioration in a laboratory test value or vital sign is associated with clinical signs and symptoms, the clinical sign or symptom should be reported as an AE and the associated laboratory test result or vital sign will be considered additional information. Wherever possible, the reporting investigator should use the clinical term rather than the laboratory term (eg, “anemia” versus “low hemoglobin value”). In the absence of clinical signs or symptoms, clinically-relevant deteriorations in nonmandated parameters should be reported as AE(s).

Any new or aggravated clinically-relevant abnormal medical finding at a physical examination as compared with the baseline assessment will be reported as an AE (baseline data are collected at Visit 2).

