4.3.3.5 Vital Signs

Vital signs (body temperature, blood pressure [BP], pulse rate, and respiratory rate) will be evaluated at screening, and at various time points as outlined in Table 5, Table 6, Table 7, Table 8, Table 9, and Table 10.

Vital signs should be within 60 minutes prior to investigational product administration, every 15 minutes (\pm 5 minutes) during the infusion, immediately (+ 5 minutes) after the end of the infusion, and then every 30 minutes (\pm 5 minutes) for 2 hours after dosing or until stable, whichever is later.

Any abnormalities should be reported as AEs or signs/symptoms of NMO/NMOSD as applicable.

It is important that body temperature is assessed in order to evaluate the subjects of any signs of infection or infusion reaction, especially when assessing for potential attacks.

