5 ASSESSMENT OF SAFETY

5.1 Definition of Adverse Events

The ICH Guideline for Good Clinical Practice (GCP) E6(R1) defines an AE as:

Any untoward medical occurrence in a patient or clinical investigation subject administered a pharmaceutical product and which does not necessarily have a causal relationship with this treatment. An AE can therefore be any unfavorable and unintended sign (including an abnormal laboratory finding), symptom, or disease temporally associated with the use of a medicinal product, whether or not considered related to the medicinal product.

An AE includes but is not limited to any clinically significant worsening of a subject’s pre-existing condition. An abnormal laboratory finding (including ECG finding) that requires medical intervention by the investigator, or a finding judged by the investigator as medically

significant should be reported as an AE. If clinical sequelae are associated with a laboratory abnormality, the diagnosis or medical condition should be reported (eg, renal failure, hematuria) not the laboratory abnormality (eg, elevated creatinine, urine red blood cells increased). Abnormal laboratory values that are not, in the investigator's opinion, medically significant and do not require intervention should not be reported as AEs.

Adverse events may be treatment emergent (eg, occurring after initial receipt of investigational product) or nontreatment emergent. A nontreatment-emergent AE is any new sign or symptom, disease, or other untoward medical event that begins after written informed consent has been obtained but before the subject has received investigational product.

Elective treatment or surgery or preplanned treatment or surgery (that was scheduled prior to the subject being enrolled into the study) for a documented pre-existing condition that did not worsen from baseline is not considered an AE (serious or nonserious). An untoward medical event occurring during the prescheduled elective procedure or routinely scheduled treatment should be recorded as an AE or SAE.

For the purposes of this protocol, NMO/NMOSD attacks will not be recorded as an AE during either the RCP or the OLP. Symptoms that are subsequently diagnosed due to another underlying cause will be recorded as AEs.

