3.7.1.1 Adverse Events of Special Interest

The following Adverse Events of Special Interest (AESI) will be summarized; the infusion related reaction, anaphylactic reaction and hypersensitivity will be collected from the case report form. Infections will be identified by the corresponding System Organ Class (SOC); for remaining AESIs, relevant search criteria will be established prior to database lock.

- Infusion Related Reaction
- Anaphylactic Reaction
- Hypersensitivity
- Infections
- Hepatic Function Abnormality
- Cytopenia
- Opportunistic Infection
- Progressive Multifocal Leukoencephalopathy (PML)

Symptoms corresponding to infusion-related reaction will be summarized separately and will not be combined with TEAE analysis.

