3.7.4.2 Vital Signs

Change from Baseline in the following vital sign parameters will be collected in this study: systolic blood pressure, diastolic blood pressure, body temperature, pulse rate, and respiratory rate.

Vital signs data will be summarized by visit and by treatment group using descriptive statistics. For vital sign assessments collected on the dosing day, the vital sign data will be presented by time points of interest as well. The time points of interest are as follows:

- Pre-dose assessment;
- During dose assessment: 15min, 30min;
- After dose assessment: immediately after dosing, the last assessment before discharge.

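### Protocol Section 5.1 and Appendix 12 set different thresholds for recording a protocol-mandated laboratory change as an adverse event, so counts of non-serious cytopenia and lesser liver elevations depend on which text a site follows

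*Protocol*

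**What the plan says.** Three parts of the protocol govern the same measurements.

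- **Section 5.1 (definition of AEs).** The positive rule reads "An abnormal laboratory finding (including ECG finding) that requires medical intervention by the investigator, or a finding judged by the investigator as medically" significant, is to be reported. The matching exclusion is "Abnormal laboratory values that are not, in the investigator's opinion, medically significant and do not require intervention should not be reported as AEs". These sentences cover laboratory and ECG findings; they do not name vital signs.
- **Appendix 12 (examinations and tests).** The rule for scheduled measurements begins "Deterioration in protocol-mandated laboratory test values or vital signs compared to baseline should only be reported as AEs if they fulfill any of the". It leaves two routes to an AE: a criterion of seriousness, or stopping of investigational product. For tests outside the schedule the threshold is lower: "In the absence of clinical signs or symptoms, clinically-relevant deteriorations in nonmandated parameters should be reported as AE(s". Where a change comes with clinical signs or symptoms, the sign or symptom is the AE.
- **Section 4.3.3.5 (vital signs).** "Any abnormalities should be reported as AEs or signs/symptoms of NMO/NMOSD as applicable". Sections 4.3.3.3 (weight) and 4.3.3.4 (ECG) carry a similar sentence.

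Section 5.4 sends the investigator to Appendix 12 for severity and relationship, not for the reporting threshold. No section gives an order of precedence.

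Treatment-emergent AEs are a secondary endpoint (Protocol Section 2.2.2). SAP Table 3.7.2.2-1 tabulates them by SOC and PT, by grade and by relationship, and tabulates AESIs. SAP Section 3.7.1.1 lists cytopenia and hepatic function abnormality as AESIs and leaves their definition open: "for remaining AESIs, relevant search criteria will be established prior to database lock".

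**The concern.** A site working from Section 5.1 and a site working from Appendix 12 can see the same laboratory result and record different things, each in line with the protocol. The restrictive sentence sits in an appendix that Section 5.4 cites for another purpose, so some sites may apply it and others may never see it. The threshold is also the reverse of what one would expect: a clinically relevant change in an unscheduled test is reportable, while the same change in a scheduled test is not.

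At stake are the AE tables for laboratory-based terms. For a B-cell depleting antibody, cytopenia and liver changes are among the findings that readers of those tables will look for.

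**Working it through.** The documents give no rate for the affected findings, so there is no figure to reproduce. The check is a comparison of what each rule does with a protocol-mandated laboratory value.

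| Type of finding | Section 5.1 | Appendix 12 |
|---|---|---|
| Meets an SAE criterion, including every Hy's law case (Section 5.6.2) | AE | AE |
| Leads to stopping product, for example under the limits in Section 4.1.6 | AE (significant in practice) | AE |
| Comes with clinical signs or symptoms | Clinical condition recorded | Clinical sign or symptom recorded |
| Neither significant nor treated | Not an AE | Not an AE |
| Non-serious, asymptomatic, judged significant, product not stopped | **AE** | **Not an AE** |

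Only the last row differs. Two examples fall in it:

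1. *Neutrophils.* A low count that the investigator considers significant and follows with repeat counts, that is not serious, and that does not meet the neutropenia stopping rule in Section 4.1.6.
2. *Liver.* ALT or AST between 3 and 5 times ULN, bilirubin no more than 2 times ULN, INR no more than 1.5, no symptoms and no eosinophilia above 5%. This is below Hy's law and below each liver limit in Section 4.1.6. If judged significant, it is an AE under Section 5.1 only.

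For vital signs the comparison is between Appendix 12 and Section 4.3.3.5. An isolated, asymptomatic, non-serious abnormality that does not stop product is reportable under Section 4.3.3.5 and not under Appendix 12.

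**Effect on the tables.** Let *q* be the fraction of last-row findings that reach the AE form, and assume it is the same in both arms. The recorded rate in each arm is then *q* times the true rate. The ratio between arms is unchanged, and the absolute rate and the difference between arms are both multiplied by *q*. If every site followed Section 5.1, *q* would be 1; if every site followed Appendix 12, it would be 0. The documents do not locate *q* between those limits or say how common last-row findings are.

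**What is preserved.** SAP Section 3.7.3 grades laboratory values by CTCAE version 4.0 in the RCP and OLP and tabulates worst grade, shifts and Grade 3-4 toxicities. These tables do not depend on AE reporting.

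**The case against.** The strongest reply is that Appendix 12 has a rationale: scheduled results are summarised in the study report anyway, so recording them again as AEs adds little. SAP Section 3.7.3 supports this. Recording is masked and the same rules apply in both arms. The AESI search criteria are also still open and could include laboratory values. All of this stands and limits the harm. It does not remove the conflict, because Section 5.1 is the protocol's definition of an AE, and the AE and AESI tables are reported in their own right.

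Several stronger readings are tempting, and the documents do not support them.

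- *That the two rules are opposites.* They agree in four of the five rows above.
- *That outpatient-treated Grade 3 neutropenia is clearly lost under Appendix 12.* The important-medical-event criterion in Section 5.2 gives intensive treatment of blood dyscrasias at home as an example, so such a case may be serious and reportable under both rules. The monitored, untreated case is the secure example.
- *That the protocol's hepatic AESI is undercounted.* Section 5.3 limits it to Hy's law cases, which are always SAEs. Only lesser elevations are exposed.
- *That infusion-reaction counts are affected.* SAP Section 3.7.1.1 takes these from the case report form, and a reaction with signs or symptoms is an AE under either rule.
- *That after the Day 15 dose only SAE-level laboratory changes can be recorded in the RCP.* Associated clinical signs remain reportable. Stopping product under Section 4.1.6 also bars OLP dosing, and for completers OLP Day 1 should be the same day as Day 197 (Section 4.2.2.2).
- *That the SAP's limited infusion time points ("During dose assessment: 15min, 30min") are part of the same fault.* That is a choice of display. SAP Section 3.7.4.2 also has a reading immediately after dosing, and all data are listed.

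**Conclusion.** The conflict is real and unresolved, but narrow. It affects non-serious, asymptomatic changes in protocol-mandated laboratory values that an investigator judges significant and that do not stop product. For vital signs it affects the corresponding isolated abnormalities, through Section 4.3.3.5. Treatment-emergent AE counts for cytopenia and lesser hepatic terms may be too low and may vary by site. The SAP's cytopenia and hepatic AESI counts share this only if the search runs on AE terms, which the SAP does not settle.

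The size cannot be computed from the documents. A reader might infer a bias between arms, but none is shown: recording is masked and follows the same text in both. The conclusion assumes that sites have no separate instruction on precedence, such as completion guidelines outside these documents.

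**What to change.** 1. **Protocol.** Reconcile Section 5.1, Sections 4.3.3.3 to 4.3.3.5 and Appendix 12 into one recording rule and state which text prevails. The most natural way is to delete the restrictive Appendix 12 sentence and refer to Section 5.1 from there and from Sections 4.3.3.3 to 4.3.3.5. Because Section 5.1 does not name vital signs, add them to it. Tell sites by memo.
2. **SAP Section 3.7.1.1.** Define the cytopenia and hepatic AESIs from central-laboratory CTCAE grades as well as AE terms, and show the two sources separately. Fix the grades and terms before unmasking.

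The first change helps only data still to be collected. Amendment 6 already provides for stopping enrollment and moving RCP subjects to the OLP, so new wording cannot repair RCP AEs already recorded. The second change does cover that period, because it uses laboratory results already held. It does not reach far into the SFP, where Table 10 schedules no routine haematology or chemistry.

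The cost is protocol wording, a site memo and a few tables. More laboratory AEs will be recorded, and the recording rule will change part-way through the study. The report should give the date of the change and avoid reading a rise in laboratory AEs after it as a drug effect.

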Figure 2.3-1	Study Flow Diagram.....	16
Figure 3.3.1-1	Subject Disposition.....	23
Figure 3.7.1-1	Visual definition of TEAEs during different study periods.....	45
Figure 7-1	Neuromyelitis Optica Spectrum of Disorders Relapses Before and After Treatment with Azathioprine for 70 Patients with More Than 12 Months Follow Up.....	61
Figure 7-2	Attack Frequency Before, During, and After Eculizumab Treatment.....	62
Figure 7-3	Relapses in Patients with Neuromyelitis Optica Before and After Treatment with Rituximab.....	62
Figure 7-4	Disease Course of Patients Treated with Rituximab.....	63
Figure 7-5	Relapses in Patients with Neuromyelitis Optica Before and After Treatment with Rituximab.....	64
Figure 7-6	Estimated Predictive Power Against Observed Interim Treatment Effect When 50% of AC-determined NMO/NMOSD Attacks are Available.....	66
Figure 7-7	Multiplicity Adjustment Strategy.....	68
Figure 7-8	Agreement between Investigator and AC determination of Attacks.....	75

LIST OF APPENDICES

Appendix 1	Sample Size Calculation.....	60
Appendix 2	Details of Futility Analysis.....	68
Appendix 3	Type I Error Control.....	69
Appendix 4	Neuromyelitis Optica Attack Severity Score.....	71
Appendix 5	WMWodds approach for mRS score analysis.....	75
Appendix 6	Kappa Statistic for Investigator and AC-determined Attack Agreement.....	77

Amendment History

Date	Description of Change
October 18, 2018	
 • Amendment History: Oct 19, 2016 should be Oct 31, 2016 • Sections 2.2.1, 2.2.1.1, 2.2.1.3, 2.2.1.4 and 3.4.1.3: Introduced language related to changes in the study resulting from the Sponsor’s decision to accept recommendations from the DMC, based on evidence of efficacy and safety, to stop study enrollment and allow subjects in the RCP at that time the option to enter the OLP • Section 3.1.3: Only major protocol deviation will be summarized by category. • Section 3.4.1.4: A sensitivity analysis of the primary efficacy endpoint was added to analyze the date up to and including January 27, 2017.
September 12, 2018	
 • Analysis of flow cytometry data was removed from Table 3.2-2 for Any MEDI-551 Population as data not being collected • Table 3.3.2.4-1: Annualized relapse rate prior to 1st IP administration instead of prior to randomization will be calculated • Table 3.3.2.4-1: Analysis of “Time (days) in between consecutive relapses, overall and by each type of relapse” was removed • Analysis of total number of T2 lesions by location was removed from Table 3.3.2.4-1 as data not being collected • Section 3.3.3: Remove “excluding placebo dose at OLP Day 15” from “Extent of Exposure” definition for more clarity • Section 3.3.4.1: Definition of concomitant medication was revised to reduce ambiguity • Section 3.4.1.4: Additional and Sensitivity Analyses of the Primary Efficacy Endpoint: Two sensitivity analyses of the primary endpoint added to 1) include SFP attack data for subjects who prematurely discontinue the RCP; and 2) censor subjects with attack onset on or before Day 15 • Section 3.4.1.6: “the negative percent agreement (NPA) = $100 \times \frac{d}{b+d} = 100\%$ as b=0 (no AC attack determination if there is no investigator’s determination)” was revised to “the negative percent agreement (NPA) = $100 \times \frac{d}{b+d}$” • Section 3.5.1.1: “percent change from baseline” was removed from the analysis of pain scale by visit as most of subjects experienced no pain at baseline. • Section 3.7.1: Typos in the Definition of Treatment-Emergent AEs for RCP period were corrected • Table 3.7.2.2-1: “TEAEs by System Organ Class (SOC)” and “TESAEs by SOC” were removed as the summary data are redundant • Table 3.7.2.2-1: Summary table “IP Related TEAEs with Severity ≥ Grade 3 by SOC and PT” was added • Section 3.7.4.4: “Change from baseline in body weight” analysis for OLP was removed as the data not being collected

	
 Section 3.9: Individual MEDI-551 concentration plots by AQP4-IgG seropositive and seronegative subjects were removed
Feb 27, 2017	
 Updated the study overview in Section 2.2 per Protocol Amendment 4 Sample size was increased from 212 subjects to 252 subjects in Section 2.4 and Appendix 1 Masked sample size reassessment was removed from Section 5 and Appendix 3 The data cut-off date for the primary analysis was defined in Section 3.4.1.3 The censoring date for subjects who discontinue early or who complete the RCP without an AC-determined NMO/NMOSD attack was clarified in Section 3.4.1.3 SF-36 domain and summary score calculations were removed from Appendix 5 and stated in Section 3.5.2 that the scores will be calculated by Optum™ Minor edits were addressed
Oct 31, 2016	
 Updated the study overview in Section 3 per Protocol Amendment 3 Clarified the masked sample size reassessment in Section 5.1 Clarified futility stopping rules in Section 5.2. Added sensitivity analysis to evaluate the impact of attack assessment window per FDA Type A meeting minutes in Section 3.4.1.4 Added the time point of interest on a dosing data for vital signs data analysis in Section 3.7.4.2

